3.1. Eligibility Criteria

- 3.1.1. Patient has platinum-sensitive, recurrent ovarian, fallopian-tube or peritoneal cancer. Platinum sensitivity is defined as complete clinical remission after frontline chemotherapy lasting greater than 6 months
- ^{3.1.2.} Patient has completed at least 2 courses of platinum-based chemotherapy with a PR or CR as defined by the Response Evaluation Criteria in Solid Tumors (RECIST) v1.1³⁹ or a CA-125 response, according to Gynecological Cancer InterGroup (GCIG) criteria⁴⁰
- 3.1.3. BRCA testing required (results not needed for registration)
- 3.1.4. Age ≥ 18 years old
- 3.1.5. ECOG performance status score of 0, 1, or 2 (See Appendix A)
- 3.1.6. Life expectancy greater than 6 months
- 3.1.7. Normal organ and marrow function as defined below:
 - Absolute neutrophil count (ANC) \ge 1.5 x 10⁹/L
 - Platelets $\geq 100 \text{ x } 10^9/\text{L}$
 - Hemoglobin (Hgb) \geq 8 g/dL (blood transfusions to reach this amount are allowed)

- Serum creatinine $\leq 1.5 \text{ mg/dL}$
- Total serum bilirubin $\leq 1.5 \text{ x ULN}$

-AST and ALT \leq 2.5 x ULN

- 3.1.8. Able to take oral medication
- 3.1.9. Not pregnant and not breastfeeding
- 3.1.10. Able to understand and willingness to sign a written informed consent document
- 3.1.11. Patients must be enrolled within 8 weeks of completing last cycle of chemotherapy

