11. STUDY CALENDAR

Baseline evaluations are to be conducted within 14 days prior to start of trial. Imaging CT scans and x-rays must be done ≤ 4 weeks prior to the start of therapy.

Procedure/Test	Pre- Study	Surveillance every 4 weeks	Day 1 of each cycle	Every 12 weeks	30 day follow- up*	Every 3 months
Informed consent	Х					
Demographics	Х					
Concurrent medications	Х	Х	Х		Х	
Medical history	Х					
Physical exam ^A	Х	Х	Х		Х	
Vital signs ^A	Х	Х	Х		Х	
Height and Weight ^A	Х	Х	Х		Х	
Performance status ^A	Х	Х	Х		Х	
CBC w/diff, platelets A	Х		Х		Х	
Serum chemistry A,B	Х		Х		Х	
CA125 ^A	Х	Х	Х		Х	
PTT/PT/INR ^C	Х					
EKG ^C	Х					
Tumor Measurements D	Х			Х		
Baseline signs & symptoms	Х					
Adverse event evaluation ^E	Х	Х	Х		Х	
Worry and Distress Measures ^F	Х	Х	Х		Х	
Quality of Life and Physical Function Measures ^G	Х			Х	Х	
Financial Toxicity Measures ^H	Х			Х	Х	
Urine or serum B-HCG for WOCBP ¹	X					
Tissue Collection ^J	Х				Х	
PK plasma sample ^K			ХК			

BRCA testing ^L	X			
Survival Follow-up ^M				Х

*Patients should be seen 30 days after completion of treatment to assess for resolution of toxicity

- A. These procedures do not need to be repeated in cycle 1 if done pre-study within 7 days prior to start of protocol therapy.
- B. Albumin, alkaline phosphatase, total bilirubin, direct bilirubin, bicarbonate, BUN, calcium, chloride, creatinine, glucose, potassium, total protein, SGOT [AST], SGPT [ALT], sodium, magnesium, phosphorus
- C. Required pre-study, then as clinically indicated
- D. Prior to olaparib initiation, imaging will only be done for doubling of nadir CA125 or per physician discretion for patient symptoms. Following initiation of olaparib, CT scans will be obtained every 12 weeks as part of surveillance. CT scans can be obtained for rising CA125 or physician preference for patient symptoms before scheduled routine surveillance.
- E. Adverse event evaluation will include both the CTCAE and the PRO-CTCAE (See Appendix D).
- F. Worry and distress measured via Assessment of Survivor Concerns (ASC) (See Appendix E) worry subscale and Impact of Event Scale (IES-R) (See Appendix F).
- G. Health-related quality of life will be measured via The Functional Assessment of Cancer Therapy + Ovarian-specific scale (FACT-O) (See Appendix G) and physical function assessed through the PROMIS Physical Function-20a assesses self-reported performance of physical activities (See Appendix H).

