13.2 SAMPLE SIZE/ACCRUAL RATE

Study 19 is the only PARP inhibitor maintenance trial in the platinum sensitive recurrent setting to report both PFS and OS data. Median progression-free survival was 8.4 months in the olaparib group versus 4.8 months in the placebo group (hazard ratio for progression or death, 0.35; 95% confidence interval [CI], 0.25 to 0.49; P<0.001). The secondary end point of time to progression according to the RECIST guidelines or CA-125 level, whichever showed earlier progression, was also significantly longer in the olaparib group than in the placebo group (median, 8.3 months vs. 3.7 months; hazard ratio for progression, 0.35; 95% CI, 0.25 to 0.47; P<0.001). There was no statistically significant OS advantage noted for those treated with olaparib; for the entire population median OS was 29.8-months-[95%-CI-26·9–35·7]-in the olaparib arm vs 27.8 months-[24·9–33·7] in the placebo arm. For those patients evaluable for response (n=61), there were 16 (26.2%) either PR or CR by RECIST and 1 (1.6%) by CA125²⁹.

Using the reported data from Study 19, we will assess whether delaying olaparib until biochemical relapse will increase the median time to next treatment by \sim 3 months (from 8 to 11 months). We assume 3-4 patients can be accrued/month and that the *BRCA* mutation

prevalence will be ~20% and thereby be comparable to the historical control group. With 2 years of accrual and 18 months of additional follow up, we will require 75 eligible patients. This will allow 90% power for a level 0.10 one-sided one sample exponential test to detect an improvement in median time to next treatment from 8 to 11 months. Due to the possibility of lost to long-term follow-up, we plan to accrue an additional 10% of the targeted accrual. Therefore, the sample size for this study will be approximately 83 patients in order to successfully accrue 75 evaluable patients.

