13.3.5 Analysis of Patient Reported Outcomes, Quality of Life and Financial Toxicity Endpoints

Additional **Secondary Endpoints** include a series of quality of life instruments and financial toxicity measures. These instruments will be administered starting at onset of trial enrollment and periodically thereafter. Patient reported adverse events, worry and distress (3 instruments measured every 4 weeks), health related quality of life, physical functioning and financial toxicity (5 instruments measured every 12 weeks) will provide data for longitudinal analysis with mixed effects linear models. We will focus on change over time particularly between the two treatment periods, pre and post olaparib. Our linear mixed effects models will emphasize random coefficients that allow non-linear profiles, typically polynomial regression, restricted cubic splines or piecewise linear splines with a knot to represent the time of starting olaparib. These models will permit us to estimate whether quality of life and financial toxicity change over the course of the clinical trial and, in particular, whether the observed change suggests a shift that is consistent with the start of olaparib therapy.

For drug exposure measured through quantitating olaparib by LC-MS/MS in a trough sample, trough concentrations between groups will be compared with non-parametric Wilcoxon signed rank test with significance set at P<0.05. If significant, we may explore ROC analyses.

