APPENDIX I: Collection of Indirect and Nonmedical Direct Costs (Modified COIN)

Subject ID:	
Date Completed:	

PRELIMINARY INFORMATION

1. What was your employment status at the time your cancer was diagnosed?

O Working full time

O Working part time

0 Homemaker

O Disabled

O Unemployed and seeking work

O Retired

O Student

O Other; specify: _____

2. What best describes your occupation at the time of your cancer diagnosis? If you were not employed, which category best describes your last job?

O Professional, technical (e.g., teacher, lawyer, physician, engineer)

O Manager, administrator or proprietor (e.g., manager, real estate agent, postmasters)

O Clerical and related (e.g., secretary, clerk, mail carrier)

O Sales occupations (e.g., sales person, demonstrator, agent or broker)

- O Service occupations (police, cook, hairdresser)
- **O** Skilled crafts, repair work (e.g., carpenter, telephone line worker)

O Equipment or vehicle operator (e.g., driver, brakeman)

O Laborer (e.g., helper, longshoreman, warehouse worker)

O Farmer (owners, managers, operators, tenants)

O Military

O Homemaker

O Not working

O Other; specify:

3. Which category best describes your gross/before taxes earnings at the time

Your cancer was diagnosed? (your average income from your job, as opposed to income from interest on investments)

- O Less than \$10,000
- **O** \$10,000---\$19,000
- **O** \$20,000---\$39,000
- **O** \$40,000---\$59,000
- O \$60,000---\$79,000
- **O** \$80,000---\$99,000
- **O** \$100,000---\$150,000
- **O** Over \$150,000
- 4. What type of health insurance did you have at the time of your cancer diagnosis?
- O Medicaid
- O Medicare
- O Disability insurance
- **0** HMO
- O Individual health insurance
- O Group health insurance
- **O** National health insurance
- **O** VA/military sponsored
- **O** No insurance (self pay)
- O No insurance, no means of payment
- 5. What is your current employment status?
- O Currently working full time
- O Currently working part time
- 0 Homemaker
- \mathbf{O} Disabled
- **O** Unemployed and seeking work
- 0 Retired
- O Student

O Other; specify:

6.	If you are not working, when did you stop?	/	 	/
N/A	A (Not Applicable); presently working			

OUT---OF---POCKET COSTS

Please indicate the number of times the following services were used OVER THE LAST MONTH related to your cancer care, whether it was covered all or in part by your insurance, and the out of pocket costs to you (including co---payments).

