APPENDIX J: Economic Hardship

ID:	
Date	
Completed:	

Please circle or check one answer that best applies to you.

Financial Strain

	Almost Never	Once i While	n a Somet		ot of the time frequently)	Almost Always
In the next three months, how often do you think that you and your family will experience bad times such as poor housing or not having enough food?	1	2	3		4	5
In the next three months, how often do you expect that you will have to do without the basic things that your family needs?	1	2	3		4	5
Inability to Make Ends M	de	great al of ficulty	Quite a bit of difficulty	Some difficulty	A little difficulty	No difficulty at all
Think back over the past 3 months and tell us how much difficulty you had paying your bills. Would you say you had		1	2	3	4	5
		ough ney	Some money left	-	h Somewhat; ft short of money	-
Think again over the past months. Generally, at the end of each month did yo end up with	3 1	-	2	3	4	5
Not Enough Money for N	ecessities					

Please think about how you Felt about your family's

economic situation over thee past 3 months. Indicate how much you would agree or					
disagree with each statement.	Strongly agree	Agree	Neutral/mixed	Disagree	Strongly disagree
My family had enough money to afford the kind of home we should have.	1	2	3	4	5
We had enough money to afford the kind of clothing ae should have.	1	2	3	4	5
We had enough money to afford the kind of furniture or household appliances we should have.	1	2	3	4	5
We had enough money to afford the kind of car we need.	1	2	3	4	5
We had enough money to afford the kind of food we should have.	1	2	3	4	5
We had enough money to afford the kind of medical care we should have.	1	2	3	4	5
My family had enough money to afford leisure and recreational activities.	1	2	3	4	5
Economic Adjustments/Cutba In the last 3 months, has your j made any of the following adju because of financial need?	family		Yes 1	No	2
Changed food shopping or eat a lot to save money	ing habits				
Shut down the heat or air conc to save money even though it the house uncomfortable	-				

Didn't go to see the doctor or Dentist when you needed to Because you had to save money

Fell far behind in paying bills

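### No quality-of-life, physical function or financial form is tied to the first olaparib dose, although the analysis looks for a shift at that point and the 12-week clock has no stated anchor

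*Combined protocol and SAP*

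**What the plan says.** Section 13.3.5 starts the patient-reported instruments at enrollment. It lists three that are collected every 4 weeks (PRO-CTCAE and the two worry and distress scales) and, for quality of life, physical function and financial toxicity, "5 instruments measured every 12 weeks". All feed linear mixed models that concentrate on the periods before and after olaparib. One option named is "piecewise linear splines with a knot to represent the time of starting olaparib", and the stated aim is to see whether any change fits the start of the drug.

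The Section 11 calendar marks the rows as follows:

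| Row | Pre-study | Surveillance, 4-weekly | Day 1 of each cycle | Every 12 weeks | 30-day follow-up |
|---|---|---|---|---|---|
| "Quality of Life and Physical Function Measures" | yes | no | no | yes | yes |
| Financial toxicity measures | yes | no | no | yes | yes |
| Worry and distress measures | yes | yes | yes | no | yes |
| Adverse events, including PRO-CTCAE | yes | yes | yes | no | yes |

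The calendar does not say when the 12-week count begins. For CT, the other item in that column, footnote D counts from olaparib initiation.

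On timing, Section 3.1.11 says "Patients must be enrolled within 8 weeks of completing last cycle of chemotherapy". Sections 5 and 6.1 start olaparib when CA125, checked every 28 days, has doubled, and a CT is done first. The trial has one arm.

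**The concern.** The analysis is built around the first dose, yet for these five instruments that is a time at which nothing is scheduled. The only pre-olaparib value that every patient is sure to have is the enrollment one, taken within 8 weeks of chemotherapy. If it still carries some effect of that treatment, later recovery could hide a fall on olaparib. If the last form is several weeks old at the first dose, a decline caused by relapse in the interval falls between the last pre-drug and first on-drug values and can look like an olaparib effect.

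Recall periods add to this. COIN asks how often "services were used OVER THE LAST MONTH", so a form completed 5 or 9 weeks before the first dose misses the last off-drug month. Economic Hardship includes "Think back over the past 3 months and tell us how much difficulty you had paying your bills", so on an enrollment clock the first form after the start can cover both off- and on-drug time.

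Objectives 1.2.6, 1.2.7 and 1.2.9 draw on these instruments. A value not collected at the first dose cannot be recovered later.

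**Working it through.** The plan states no power or precision for these analyses, so there is no figure of its own to reproduce. The check counts the pre-olaparib forms that the schedule yields.

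**Inputs**
- Forms every 12 weeks and CA125 every 4 weeks (Sections 13.3.5, 5 and 11).
- Time from enrollment to trigger: the documents do not give it. The proxy is the Study 19 placebo arm's time to RECIST or CA-125 progression in Section 13.2 (Sample size/accrual rate), "median, 8.3 months vs. 3.7 months", where 3.7 is the placebo figure. The range runs from 2.5 months (assumed) to 4.8 months (placebo PFS, same section).
- Assumptions: exponential time to trigger, detection at the next 4-weekly visit, first dose one week after detection.

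**Reading A: 12-week clock from enrollment.** One month is 365.25/12/7 = 4.35 weeks, so 3.7 months is 16.1 weeks. A patient detected at week 4 or 8 starts before the week-12 form and has only the enrollment value:

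Share = 1 − 2^(−8/16.1) = 29%, or about 22 of 75 patients.

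The gap from the last form to the first dose depends on where detection falls between forms: on a form visit (0 + 1 = 1 week), 4 weeks after one (4 + 1 = 5) or 8 weeks after one (8 + 1 = 9). With p = 2^(−4/16.1) = 0.842:
- 5 weeks: (1 − p)/(1 − p³) = 0.39
- 9 weeks: 0.39 × p = 0.33
- 1 week: 0.39 × p² = 0.28
- Mean: 5 × 0.39 + 9 × 0.33 + 1 × 0.28 = 5.2 weeks

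| Assumed median to trigger | Enrollment value only | Two or more pre-olaparib forms | Mean gap to first dose |
|---|---|---|---|
| 2.5 months | 40% | 60% | 5.3 weeks |
| 3.7 months | 29% | 71% | 5.2 weeks |
| 4.8 months | 23% | 77% | 5.2 weeks |

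At 3.7 months, 42% have three or more forms and the mean is 2.8.

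**Reading B: 12-week clock from olaparib start, as for CT.** Every patient has exactly one pre-olaparib value, the enrollment one. No pre-olaparib slope can be estimated within a patient.

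**How much a Day 1 form helps.** This is an illustration on assumed inputs: 75 patients, within-patient correlation 0.5, 36 weeks on drug, no true drug effect, a 0.3 SD decline over the 8 weeks before the trigger, olaparib starting at the trigger visit, and a model with a knot and a level shift there. At a 3.7-month median the shift wrongly credited to olaparib is:
- −0.22 SD on the enrollment clock
- −0.26 SD with only the enrollment value before the drug
- −0.18 SD with 4-weekly forms
- −0.14 SD on the enrollment clock plus a form at the trigger (standard error 0.117, against 0.125 without it)

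A direct comparison of Day 1 with later values would show no false change here, but only because the assumed decline stops at the trigger. Real relapse need not stop there.

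**The case against.** Four things can be said for the plan with some force.

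First, under Reading A about 71% of patients have at least two pre-olaparib forms. A mixed model pools patients with staggered starts and does not need a slope from each. This stands: a reader might infer that most patients have almost no pre-olaparib data, and on an enrollment clock the figures do not support that. A reader might also suppose that the last form can be as much as 12 weeks old at the first dose. With 4-weekly detection and a one-week lag the maximum is 9. Pooling does not help under Reading B, where no patient has a second pre-olaparib value.

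Second, confounding of drug with relapse comes from starting olaparib at CA125 doubling in a single arm. It affects the 4-weekly instruments too. This also stands. It would be tempting to read the missing form as the cause, or a Day 1 form as isolating the drug effect; neither is supported.

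Third, the objectives concern the impact of a delayed-start strategy, and Section 13.3.5 also asks about change over the whole trial and speaks only of a shift consistent with olaparib start. So the objectives do not fail for want of this form. It is the before/after part of the analysis that is weakened.

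Fourth, chemotherapy carry-over at enrollment is possible, not shown: FACT-O looks back 7 days and COIN one month, while enrollment may come up to 8 weeks after chemotherapy.

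The pre-study column does not rescue the schedule. Some of its items are timed to therapy, but Section 13.3.5 places the first questionnaires at enrollment.

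**Conclusion.** The point holds as a gap in scheduling and definition. For five secondary instruments no assessment is tied to the first dose, and the 12-week anchor is undefined. Counted from enrollment, roughly a quarter to two fifths of patients (23% to 40%, 29% at the central assumption) have only the enrollment value, and the last form is on average about 5 weeks old at the first dose. Counted from olaparib start, all patients have a single pre-olaparib value. The percentages rest on a placebo-arm proxy from another trial, an exponential shape and an assumed one-week lag. The absence of a form at the first dose rests on the calendar alone.

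A Day 1 form makes the before/after comparison better defined and less exposed to relapse, but change from Day 1 onward still cannot be called an effect of olaparib alone. This is a cheap improvement to secondary endpoints and does not bear on the primary analysis.

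**What to change.** In the Section 11 calendar, add FACT-O, the PROMIS physical function form, COIN, Economic Hardship and COST at Cycle 1 Day 1, before the first dose. State that 12-weekly forms run from enrollment during surveillance and that the clock restarts at Cycle 1 Day 1.

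In Section 13.3.5, make the Cycle 1 Day 1 value the reference for change on olaparib. Treat the Day 1 worry, distress and PRO-CTCAE values, already scheduled, in the same way. Report change up to Day 1 separately. For patients with only an enrollment value before Day 1, note that this earlier change may include recovery from chemotherapy, and that Economic Hardship recall can overlap the previous form. Describe the results as change around relapse and olaparib start together.

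The cost is one extra questionnaire set per patient who starts olaparib, at a visit that already takes place, plus a calendar edit and a few sentences in the analysis section. On the assumptions above, about 28% of patients would complete it roughly a week after a surveillance form. Every patient who starts olaparib and completes the forms would then have at least two pre-olaparib values.

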- 1.2.8. To evaluate the impact of delayed start olaparib in platinum sensitive recurrent epithelial ovarian caner with a complete or partial response to last platinum therapy on worry and distress
 - 1.2.8.1. Endpoint: Worry and distress measured via Assessment of Survivor Concerns (ASC) Worry Subscale and Impact of Event Scale (IES-R).
- 1.2.9. To evaluate the impact of delayed start olaparib in platinum sensitive recurrent epithelial ovarian cancer with a complete or partial response to last platinum therapy on financial toxicity
 - 1.2.9.1. Endpoint: Financial toxicity measured through (a) monetary measure using the Modified Collection of Indirect and Nonmedical Direct Costs (COIN), (b) objective measure of financial burden assessed using Barrera et al's Economic Hardship questionnaire⁵¹, and (c) subjective measure of financial distress will be gauged using the Comprehensive Score for Financial Toxicity (COST Measure).
- 1.2.10. To explore exposure-response relationships between olaparib exposure and toxicity/efficacy.
 - 1.2.10.1. Endpoint: Exposure as expressed by day 28 trough olaparib concentration measured by LC-MS/MS.

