exposure and toxicity/efficacy. A steady-state trough sample will be obtained around day 28. Trough concentrations (if need be corrected for time since dosing) will be compared between patients with/without response and patients with/without toxicity. This assay will be performed at the UPMC Hillman Cancer Center Cancer Pharmacokineitc and Pharmacodynamics Facility. (CPPF). The published olaparib assay has successfully been implemented and is available (Nijenhuis et al. Journal of Chromatography B, 940 (2013) 121–125). Note: plan the patient's day 28 visit such that their blood can be drawn at about the time they would otherwise take their dose, but **BEFORE** they take it. Ask patients to take bring their olaparib so they can take their dose after their PK blood draw. See appendix D for practical details.

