- H. Financial toxicity will be measured through a) monetary measure using the Modified Collection of Indirect and Nonmedical Direct Costs (COIN) (See Appendix I), b) objective measure of financial burden assessed using Barrera et al.'s Economic Hardship questionnaire (See Appendix J), and c) subjective measure of financial distress will be gauged using the Comprehensive Score for Financial Toxicity (COST Measure) (See Appendix K).
- I. Pregnancy test for women of childbearing potential (WOCBP) must be done within 24 hours prior to initiation of olaparib.
- J. Tissue collection is not mandatory. If permission granted, tissue prior to initiation on olaparib will be obtained from archival stores. If patient undergoes biopsy at the time of progression as part of standard of care, tissue will be collected after routine processing.
- K. A mandatory trough plasma sample will be obtained only once at approximately 28 days after initiation of treatment (See **Appendix L**).
- L. BRCA testing required (Results not needed for registration
- M. Chart review or office visit every 3 months for 18 months from time of enrollment

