13.3.6 Analysis of Exploratory Endpoints

DNA: BROCA or whole genome sequencing for mutational changes will be assessed in pre and post- olaparib treatment. Variant changes over time will be reported descriptively. These will be assessed against reference genome to determine pathogenic variants.

RNA: RNA-Seq analysis will be performed per a recent comparative and guideline paper⁵⁵, sequencing reads will be examined for data quality by FastQC, and aligned, assembled and annotated (gene-based and isoform-based) using HISAT2, StringTie and Ballgown⁵⁶. Differential expression analysis based on count data will be performed by DESeq2⁵⁷. Low expressed genes will be filtered (25% of genes with smallest sum of counts across all samples). Assuming significance level at 0.05, n=40 samples (20 each pre/post therapy) standard deviation at 0.1, we will have >99%. statistical power to detect a difference for a given gene with effect size=0.8. When we account for multiple testing for 10,000 genes, we still have 70% statistical power to detect a difference of effect size 3 at

Family-Wise Error Rate (FWER) of 0.05. Using False Discovery Rate (FDR) for multiple testing control (e.g. using Benjamini-Hochberg procedure) can only increase the power.

REFERENCES

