APPENDIX L: PHARMACOKINETICS SHEET DAY 28 - OLAPARIB

Phase IIA trial of delayed initi	ation of olaparib maintenance	e therapy in platinum sensitive recurr	ent ovarian cancer				
Study Sample Collection Log							
Subject Initials: (First_Middle_Last)		Subject ID:	Date:	BSA: (m²)	Site Name:		
Pharmacokinetic (PK) Sample	Collection						
At approximately Day 28, right before the patient would otherwise take their dose, ~3-4 mL of peripheral blood will be collected in a purple top tube (e.g. BD vacutainer 367861 plastic 13 x 75 4 mL tube); Invert tube to mix; centrifuge for 10 min at ~1000 x g; aspirate plasma and place into appropriately-labeled microcentrifuge tubes. After processing, store plasma at -70°C or below. At the time of sample transfer, a copy of this completed PK form must be transferred also. Note the times administering of oral dose, in this form; specifically the time of previous dose, and the time of the dose immediately after the blood draw.							
		Olaparib					
Protocol Sample and Time Point	Projected Sample Due Time (24 hr clock)	Actual Time (24 hr clock)		Commer	nts		
Day ~28 Administer the olaparib after taking the blood sample Olaparib Dose (mg):							
Time of previous olaparib dose				commonly the	night prior		
pre/trough blood sample							
Time of olaparib dose immediately after sample

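### Section 13.3.5 names a paired test (Wilcoxon signed rank) to compare single olaparib troughs between different patients; an independent-samples test such as the rank-sum test should be named instead

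*Combined protocol and SAP*

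**What the plan says.** The last paragraph of section 13.3.5 gives the only stated test for the exposure data: "trough concentrations between groups will be compared with non-parametric Wilcoxon signed rank test with significance set at P<0.05". It adds a conditional follow-on step: "If significant, we may explore ROC analyses".

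The groups are defined in section 10.1.6 (Pharmacokinetics), where troughs "will be compared between patients with/without response and patients with/without toxicity".

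The sampling is set by note K to the study calendar in section 11: "A mandatory trough plasma sample will be obtained only once at approximately 28 days after initiation of treatment". The collection log in Appendix L agrees. It has one sampling row, labelled "pre/trough blood sample", and its other timed rows record the doses before and after that draw.

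The objective served is secondary objective 1.2.10: "To explore exposure-response relationships between olaparib exposure and toxicity/efficacy".

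**The concern.** The signed rank test works on within-pair differences, or on differences from a fixed reference. The plan's comparison is between different patients, each measured once. The test named and the data collected therefore do not match.

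At stake is the prespecified analysis of one secondary objective. Section 13.3.5 sets a significance threshold for this test and makes any ROC work depend on passing it. If the named test cannot be applied, the analyst has to choose another after the data are in, and that choice is then not prespecified.

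**Working it through.** The documents give no power, effect size or sample size for the trough comparison, so there is no figure to reproduce. The check compares what the test needs with what the plan supplies.

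**What the test needs.** For pairs (x_i, y_i), form d_i = x_i − y_i, rank the |d_i|, and sum the ranks with their signs. This requires two lists of equal length with a reason for each pairing. The one-sample form replaces y_i with a fixed reference value.

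**What the plan supplies.**

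| Requirement | Where to look | What is there |
|---|---|---|
| Two values per patient | Section 11 note K; Appendix L | One trough per patient, at about day 28 |
| Matched patients | 10.1.6; 13.3.5 | No matching described |
| Reference concentration | 10.1.6; 13.3.5 | None given |
| Same patient in both groups | 10.1.6 | Not possible: with one trough, a patient falls on one side of each split |

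The possible correction for time since dosing in 10.1.6 adjusts that single value. It does not create a second one.

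**Unequal groups.** The following is for illustration only.

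- Section 13.2 plans its accrual "in order to successfully accrue 75 evaluable patients".
- The only response rate in the documents is the Study 19 figure in the same section: 16 of 61 by RECIST (26.2%), plus 1 by CA-125.
- If that rate applied and all 75 gave a trough and an evaluable response: 75 × 16/61 = 19.7, or about 20 v 55.
- Counting the CA-125 responder as well: 75 × 17/61 = 20.9, or about 21 v 54.

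With 20 values in one list and 55 in the other, the d_i do not exist. A standard software routine given lists of these lengths stops with an error.

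**Forced pairs.** Suppose 20 of the 55 were picked to make pairs. Then 55 − 20 = 35 troughs, or 35/75 = 47% of the data, would be dropped. Even with equal groups, only the sum Σd_i = Σx_i − Σy_i is fixed. The individual |d_i| and their signs change with the pairing, so the signed-rank statistic and its p-value change too. Nothing in the plan makes one pairing more correct than another.

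**Rank-sum test.** Let U be the number of cross-group pairs in which the first group's trough is higher, counting ties as one half. U uses every patient, needs no pairing, and is defined for any n1 and n2. For 20 v 55 it rests on 20 × 55 = 1,100 cross-group comparisons. The area under the ROC curve equals U/(n1 × n2), so the test and the ROC step address the same quantity.

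**The case against.** The strongest reply is that this hardly matters. The sentence in 13.3.5 speaks of groups and goes on to ROC analysis, so the two-sample intent is plain. Signed rank is probably a slip for rank sum. The error also tends to expose itself: on unequal groups the software will not run, so a wrong p-value is unlikely to be reported. The objective is worded as exploration, the ROC step is optional, and no decision in the trial depends on either. All of this stands and sets the weight of the point. It does not make the text correct, because no section names a suitable test for this comparison.

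A reader might infer more in three ways that the documents do not support:

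- **That equal groups are impossible because 75 is odd.** The number compared need not be 75. Section 12.1.1 makes response evaluability depend on at least one cycle and a 3-month CT, or on separate CA-125 conditions, and section 10.1.6 does not say how patients with and without toxicity are divided.
- **That only the rank-sum test would do.** Any valid independent-samples method would serve. Rank-sum is the closest replacement for what is written, and it fits the ROC step.
- **That a rate of misleading results can be quoted.** The documents give no trough distribution or expected difference, so any such rate would come from invented inputs.

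**Conclusion.** The point holds at low weight. As written, the test in 13.3.5 does not fit the data: 10.1.6 names two contrasts between different patients, each patient gives one trough, and there are no pairs and no reference value. This follows from sections 10.1.6, 11 (note K) and 13.3.5 with Appendix L, and rests on no assumed figures. The splits of 20 v 55 and 21 v 54 are illustrations that borrow the Study 19 response rate. The conclusion does not depend on them.

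The effect is confined to secondary objective 1.2.10 and the optional ROC step. A reader might infer that the efficacy conclusion is at risk. It is not: the one-sample exponential test of time to next treatment, and the sample size built on it, make no use of the troughs.

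**What to change.** In section 13.3.5, replace the Wilcoxon signed rank test with the Wilcoxon rank-sum (Mann-Whitney) test, for both the response and the toxicity comparison. The stated significance level and the conditional ROC step can stay as they are.

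The cost is a change of wording in one sentence. No additional samples, visits, patients or recalculation are needed.
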